Study Significance: The large bony and soft tissue tumor resections performed in musculoskeletal oncologic patients presents the potential for significant blood loss. With basic arthroplasty being associated with significant intraoperative and postoperative blood loss often necessitating blood transfusion¹, larger bony resections with the use of endoprostheses presents an even higher risk². Transfusions themselves are not without known complications. Examples include infection, hemolytic transfusion reaction, and increased short-term mortality^{1,3}. Tranexamic acid (TXA), a synthetic analog of lysine, is an antifibrinolytic that is used to reduce blood loss. TXA works by blocking the lysine binding sites on plasminogen⁴. Perioperative use of TXA has been shown to decrease intraoperative and postoperative blood loss and decrease transfusion rates in both total knee arthroplasty and total hip arthroplasty⁵⁻¹⁵. It has also been shown to result in higher postoperative hemoglobin¹³. TXA also has been shown to decrease postoperative pain, swelling, length of hospital stay, and result in higher patient satisfaction¹⁶. The proposed research is intended to show if any correlation exists between administration of TXA or not to musculoskeletal oncology patients undergoing endoprosthetic reconstruction and perioperative blood loss and blood transfusion rates. The results of this study are

important because it will serve to fill the void in the current literature as there is no current literature available that has studied TXA administration in this specific patient population.

There have been several papers written with regards to the safety of TXA in high risk patients (i.e. previous PE/VTE event).^{21,22} Whiting et al showed that in high risk patients (defined as American Society of Anesthesiologists score of III or IV) , TXA was not associated with an increase in symptomatic thromboembolic events and was associated with a decrease in transfusion rates.²² Sabbag et al showed that patients with a history of VTE had a low risk of recurrent VTE (2%) after contemporary total hip arthroplasty and total hip arthroplasty, and that rate was not increased with the use of IV TXA.²¹

Literature Review

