B. Study Type and Design: Type of Study: multi-center prospective randomized controlled trial. Study Design: We will initially monitor 4 groups of patients. The first group (20 patients) will undergo bony tumor resection of the femur or proximal tibia and endoprosthetic reconstruction with TXA. The second group (20 patients) will undergo bony tumor resection of the femur or proximal tibia and endoprosthetic reconstruction without TXA. The third group (50 patients) will undergo soft tissue sarcoma resection of the lower extremity with TXA. The fourth group (50 patients) will undergo soft tissue sarcoma resection of the lower extremity without TXA. The use of TXA is well established for arthroplasty at this institution given the body of evidence supporting both efficacy and safety. Treatment assignments will be stratified by type of resection location. Patient randomization will be done via randomization program through REDCap. The randomization process will be performed centrally at Kansas University Medical Center and the treating surgeon will not have access to the randomization list. Randomization will occur prior to definitive surgical procedure, and the treating surgeon and pharmacy will be notified to ensure adequate vials of tranexamic acid are available in the operating room (investigators/surgeons are not blinded). Patients will be blinded to treatment allocation. Those in groups using TXA will receive 1g TXA IVPB 10 minutes prior to incision and a second dose of 1g IVPB at the time of closure which is the standard protocol used for total joint arthroplasty. The TXA will be administered by the anesthesia team. If the surgeon determines intraoperatively that TXA is required for patient safety, the drug should be used. Patients receiving a non-standard dosing of TXA will then be excluded from the study. Routine hemoglobin and hematocrit measurements will be observed preoperatively as well as postoperatively at 6 hours and in the mornings of postoperative days 1-3. This laboratory regimen is currently the standard of care and utilized routinely. Patients may be discharged prior to obtaining all 4 blood draws. If a patient is discharged prior to postoperative day 3, no additional blood draw will be performed. Additionally, both intraoperative and postoperative incidents of blood transfusion will be monitored to calculate transfusion rates. Postoperative erythrocyte transfusions will be given for hemoglobin below 7.0 as is the current practice guidelines used by the attending surgeons at this institution. Other facilities are encouraged to follow this protocol, however, the ultimate decision for blood transfusion will be at the discretion of the treating physician. Surgical drains are also used routinely and their daily output will be recorded until they are deemed appropriate to pull by the attending surgeon. Patients will be clinically monitored daily while in the hospital and in subsequent follow up visits for symptoms of DVT or embolism and appropriate diagnostic screening with venous Doppler will be utilized if symptoms are present, as is also part of current routine postoperative care. Our DVT prophylaxis protocol postoperatively will be 4 weeks of aspirin 81 mg BID unless medical co-morbidities necessitate the use of other anti-coagulation. Mechanical DVT prophylaxis in the form of sequential compression devices will also be

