- Vulnerable populations as defined by the University of Kansas Medical Center IRB

Withdrawal/Termination criteria: The subject's participation will be terminated by the investigator if the subject wishes to withdrawal from the study at any point in time. In the event that a disproportionate number of complications are occurring in one of the study groups, the study will be suspended and the IRB will be consulted. There are no

safety precautions that need to be applied to subjects who withdraw from the study. The withdrawn patients will be routinely followed on an outpatient basis in a clinic setting.

E. Specific methods and techniques used throughout the study

1. Laboratory tests: Complete Blood Count (CBC) – the purpose of collection is to help determine the effect of TXA on hemoglobin and hematocrit levels. A CBC would be collected pre-operatively and post-operatively at 6 hours and in the mornings of postoperative days 1, 2, and 3. Patients may be discharged prior to obtaining all 4 blood draws. If a patient is discharged prior to postoperative day 3, no additional blood draw will be performed. Blood specimens will need to be collected for this test. This test is routinely ordered in the hospital setting and is the standard of care for evaluating and monitoring blood loss post-operatively.
2. Study Procedures: Describe each procedure to be used in the study, including the instruments used, time required for each procedure, cognitive assessments, etc. The patient's consented for this study and randomized to the TXA group will receive TXA while in the operating room as part of the routine administration of anesthesia. This is not technically considered a procedure.
3. Clearly indicate which procedures, tests, visits, etc., are parts of usual standard therapy and which are performed solely for research purposes. Make it clear which tests are routinely performed for clinical care but are providing data for the research (and are billable to insurance companies), and which tests are only performed for research purposes (not billable to insurance companies). Usual standard therapy: all postoperative clinic visits, pre-operative and post-operative CBC. These CBCs would be providing data for this clinical trial. No tests will be ordered that are only performed for research purposes.
4. Describe the fate of any body component: No body components will be obtained during this study.

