2. Primary responsibility for the following activities, for example:
 - a. Determining eligibility: [name] MD, [name] MD, [name], MD
 - b. Obtaining informed consent: [name] MD, [name] MD, [name] MD
 - c. Providing on-going information to the study sponsor and the IRB: [name] MD, [name] MD, [name]
 - d. Maintaining participant's research records: [name] MD, [name] MD, [name]
 - e. Completing physical examination: [name] MD, [name] MD, [name] MD
 - f. Taking vital signs, height, weight: Clinical support staff for participating surgeons
 - g. Drawing / collecting laboratory specimens: Clinical support staff for participating surgeons
 - h. Performing / conducting tests, procedures, interventions, questionnaires: [name] MD, [name] MD, [name] MD

- i. Completing study data forms: [name] MD, [name] MD, [name] MD, [name] MD
- j. Managing study database: [name] MD, [name] MD, [name]

L. Assessment of Subject Safety and Development of a Data and Safety Monitoring Plan

1. Please note that any study proposal with more than minimal risk must include a data and safety monitoring plan. Elements of the plan include:
 - a. Persons/groups who will review the data (study team; independent safety monitor, data monitoring committee or formal DSMB) - Study team
 - i. An independent safety monitor will be used. [name], MD is an orthopaedic surgeon familiar with the use of TXA and uninvolved with the study in any other capacity.
 - b. Data/events that will be reviewed - Adverse events/complications arising in the participating patients.
 - c. Frequency of review: Review will occur every 4 months routinely. Additionally, a review will be conducted if 5 separate adverse events are reported prior to the scheduled bi-annual review.
 - d. Types of analyses to be performed – we will analyze the rate of complications (infections, PE, DVT) between the groups to make sure that we aren't getting statistically significant differences between groups
 - e. Safety-related triggers that would cause the PI to stop or alter the study – If our analysis of complications reveals a statistically significant difference between groups, we will place the study on hold until an appropriate remedy can be reached. We will consult with the IRB before resuming the study. If no remedy can be determined the study will be permanently held

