2. Describe how adverse events and unanticipated problems will be ascertained and handled. Explain exactly which type of problems will be considered serious and reported to the IRB. The reporting timeframe should also be detailed - Sites will report serious adverse events and unanticipated problems within 72 hours to coordinating center (KUMC). The independent monitor and Primary investigator will be made aware and the independent safety monitor will determine if a further review is necessary and/or further action needs to be taken.
3. Explain exactly what will happen if a patient experiences an adverse event or other problem (for example, will discontinue study participation) - Serious adverse events will be reviewed by the independent safety monitor, principal investigator, and treating surgeon where it will be determined if study participation should be continued or not.

III. Subject Participation

A. Recruitment:

Patients that present to participating surgeons' clinics that meet inclusion criteria and do not meet exclusion criteria will be recruited for this study. The treating surgeon will conduct all of the recruitment and consent aspects of this study in his or her clinic. If the treating surgeon deems a patient to be eligible for this study based on our inclusion and exclusion criteria then these patients will be asked to participate in this study in a

noncoercive manner. We will not construct any advertisements or flyers that attempt to recruit study subjects.

Attach a copy of the recruitment letter or introductory statement and describe planned use or distribution of the document. We will not use a recruitment letter for this study.

B. Screening Interview/questionnaire: N/A. We will not use interviews or questionnaires for screening. In order to be included in this study the subjects must meet set parameters (inclusion and exclusion criteria). Evaluation of whether patients can be included in this study will be based on chart review and patient history acquisition. This will be performed by participating surgeon.

C. Informed consent process and timing of obtaining of consent

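### The one specified statistical safety comparison between arms lists infections, PE and DVT; all-cause death and embolic events other than PE should be added by arm

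*Combined protocol and SAP*

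**What the plan says.** Section II.L.1 (data and safety monitoring plan) sets out one statistical safety comparison. Under item d, "we will analyze the rate of complications (infections, PE, DVT) between the groups". The bracketed list carries no wording to suggest that it gives examples only. Item e makes the hold depend on it: "If our analysis of complications reveals a statistically significant difference between groups, we will place the study on hold". No test, significance level, denominator or interim adjustment is given.

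Other passages are wider than that list:

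- II.L.1.b, events reviewed: "Adverse events/complications arising in the participating patients".
- II.L.1.c: an extra review takes place if five separate adverse events are reported before the scheduled one.
- II.L.2: serious adverse events go to the coordinating centre within 72 hours, and "the independent safety monitor will determine if a further review is necessary and/or further action needs to be taken".
- II.D, withdrawal and termination criteria: "In the event that a disproportionate number of complications are occurring in one of the study groups, the study will be suspended". Here complications are not defined.
- II.B: patients are watched in hospital and "in subsequent follow up visits for symptoms of DVT or embolism". Embolism is not restricted to the lung.

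Sections II.C and V.A list the planned analyses. They cover blood measures, transfusion, drain output and patient factors, with no safety comparison. Mortality appears only in the background (I.B and I.C), among the harms of transfusion: "Examples include infection, hemolytic transfusion reaction, and increased short-term mortality".

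**The concern.** The events that can produce an item e hold are narrower than the events the protocol monitors and narrower than the safety question it sets itself. I.C, II.F.5 and V.B all expect a conclusive answer on whether TXA is safe in these patients. Yet if the plan is followed as written, no one is asked to set deaths, or emboli outside the lung, side by side by arm, either during the trial or at its end.

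Clot detection makes this matter more. It is driven by symptoms, and the only named test is the one in II.B: "symptoms of DVT or embolism and appropriate diagnostic screening with venous Doppler will be utilized if symptoms are present". A patient who dies of a clot that was never diagnosed adds nothing to the three listed events. At stake are the sensitivity of the interim safety check and the completeness of the final safety statement.

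**Working it through.** The plan gives no figure for the safety comparison, so there is none to reproduce. The main check is a comparison of passages; the arithmetic only shows scale.

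**Step 1. Which route would pick up which event, and is it compared by arm?**

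- *Infection, PE or DVT, diagnosed:* in the item d analysis, compared by arm, can cause an item e hold.
- *Embolic event other than PE (for example arterial):* monitored under II.B and reviewed under II.L.1.b, but not in item d.
- *Death after a diagnosed infection, PE or DVT:* the diagnosed event counts in item d; the death itself is not a line.
- *Death from an undiagnosed clot, or from another cause:* reaches the monitor under II.L.2 as a serious event and counts towards the five-event review, but is not in item d.
- *II.D suspension rule:* looks at imbalance between groups and might include deaths, but defines no events, test, threshold or schedule.

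So no passage specifies a comparison of deaths by arm.

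**Step 2. Inputs for scale.** II.C gives 20 per arm (bone) and 50 per arm (soft tissue), so 20 + 50 = 70 per arm. Assumed, because the plan is silent: Fisher's exact test, two-sided, 0.05 level. All event counts are illustrative.

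**Step 3. Illustration.** For x events against 0 with n per arm, the two-sided Fisher p-value is 2·C(n,x)/C(2n,x).

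- n=70, x=6: 2 × 131,115,985 / 9,381,724,380 = 0.028
- n=70, x=5: 2 × 12,103,014 / 416,965,528 = 0.058
- n=20, x=5: 2 × 15,504 / 658,008 = 0.047
- n=20, x=4: 2 × 4,845 / 91,390 = 0.106

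Suppose listed events occur in 5 v 5 patients of 70 per arm, and there are also 6 v 0 deaths without a listed event. The item d comparison gives p=1.0 and no item e hold; deaths on their own line give p=0.028. Pooling deaths with the listed events gives 5+6=11 v 5, p=0.18, which still hides the difference. Deaths therefore need a separate line.

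**Step 4. Effect of one unlisted embolic event.** At 70 per arm, moving from 5 v 0 to 6 v 0 takes the Fisher p-value from 0.058 to 0.028. With an uncorrected chi-squared test the step is from 3 v 0 (p=0.080) to 4 v 0 (p=0.042). Near the threshold, one embolic event outside the list can decide whether the hold is reached.

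**Step 5. How likely is the illustration?** The documents give no mortality rate. The binomial probability of 6 or more deaths among 70 is about 0.3% at an assumed 2% mortality and about 14% at an assumed 5%.

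**The case against.** The strongest reply is that the trial has other safeguards. II.D is a second rule that looks across groups and suspends the study, and its complications are not limited to three events. II.L.1.b has all adverse events reviewed. In the illustrations, the deaths would reach the monitor one by one, and would meet the five-event trigger by themselves if they fell between two scheduled reviews. Surgeons are not blinded, and nothing says the monitor is. All of this stands, and it rules out saying that deaths go unseen. It does not supply the missing comparison: II.D names no events or test, and the other routes work case by case or by total count.

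A reader might also infer that a patient who dies counts as free of complications, so that an arm with more deaths looks safer, or that fatal embolism can never affect the comparison. The documents do not support either as a general statement. A fatal PE that is diagnosed is a PE, item d does not require imaging, and an infection before death still counts. Whether a death lowers the arm's rate depends on a denominator that is not stated.

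The numerical examples are fairly criticised as built to fit: 6 v 0 and 5 v 0 are the smallest splits against zero that reach Fisher significance at 70 and 20 per arm. They show what the list can miss, not what to expect.

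Finally, counting every unexplained death as thromboembolism could misclassify deaths in a sarcoma population, and transfusion reactions are described as a risk of transfusion, not of TXA. Both objections are sound, and the fix below asks for neither.

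**Conclusion.** The point holds in a limited form. The only specified statistical safety comparison between arms, and the hold in II.L.1.e that rests on it, omit all-cause death and embolic events other than PE, and no analysis section compares these by arm. Oversight of individual deaths exists, so this is a gap in the planned comparison and not an absence of monitoring.

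Its size cannot be estimated from the documents. The illustration (p=1.0 on listed events against p=0.028 on deaths) rests on chosen counts, full enrolment, Fisher's test and a two-sided 0.05 level. The finding in Step 1 needs none of these; it follows from the wording. This is a cheap improvement.

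**What to change.** - In II.L.1.d and e, add all-cause death through the 3-month visit (the last visit in II.E.5) as its own line by arm.
- Widen the thromboembolic line to DVT, PE and any other documented arterial or venous embolic event.
- State that the denominator is all randomized patients in each arm. This needs saying because II.B excludes from the study patients who receive non-standard TXA dosing.
- Report deaths of undetermined cause separately, or as a sensitivity count, and do not classify them automatically as thromboembolism.
- Add a final safety table with the same lines to V.A.
- Reconcile the suspension rule in II.D with II.L.1.d and e so that both refer to the same events.

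The cost is protocol wording and a few table rows; deaths reported as serious adverse events already reach the coordinating centre. The downside is one or two more comparisons at each review, with a slightly higher chance of a false hold. How much higher over the whole trial cannot be worked out while the significance level and any interim adjustment are unstated.

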5. Timeline: Patients will be seen at routine post-operative visits at 2-3 weeks, 6 weeks, and 3 months where clinical examination and history taking will take place.

F. Risk/benefit assessment:

1. Physical risk: The primary concern with the use of TXA is the theoretical risk of developing a deep venous thrombosis. The patients will be monitored clinically for signs and symptoms of DVT while they are admitted to the hospital as well as at routine postoperative visits.
2. Psychological risk: We do not anticipate any psychologic risk to participants in this study.
3. Social risk: We do not anticipate any social risk in this study.
4. Economic risk: There will be no cost to subjects during this study, neither will there be any remuneration.
5. Potential benefit of participating in the study
 - a. to the individual subject and/or parent if any: None
 - b. to the population from which the subject is drawn: TXA in this patient population is sporadic and varies widely from surgeon to surgeon. Providing a definitive answer regarding the safety and efficacy of TXA in this patient population would both unify the musculoskeletal oncology field in their use or abandonment of TXA,

and potentially improve oncologic patient care in a similar fashion than that seen with the use of TXA in arthroplasty.

- c. to science, society, and humanity in general: A definitive answer regarding the safety and efficacy of TXA in this patient population would both unify the musculoskeletal oncology field in their use or abandonment of TXA

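### Study participation may be ended case by case after a serious adverse event, with unblinded input and no rule that keeps the patient's later data or assigned group

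*Combined protocol and SAP*

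**What the plan says.** All references are to the combined protocol and SAP.

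- **The rule (II.L.3).** A serious adverse event is reviewed by the independent safety monitor, the principal investigator "and treating surgeon where it will be determined if study participation should be continued or not". No criteria are given.
- **Blinding (II.B, II.C).** "investigators/surgeons are not blinded". The documents do not say whether the independent monitor sees the allocation when a case is decided.
- **Exposure (II.B).** One dose before incision and "a second dose of 1g IVPB at the time of closure".
- **Blood sampling (II.B, II.E.1).** Hemoglobin is measured before surgery, then "postoperatively at 6 hours and in the mornings of postoperative days 1-3", with no further draws after an early discharge.
- **Follow-up (II.E.5).** "Patients will be seen at routine post-operative visits at 2-3 weeks, 6 weeks, and 3 months".
- **Safety comparison (II.L.1.d).** "we will analyze the rate of complications (infections, PE, DVT) between the groups". Under II.L.1.e a significant difference puts the study on hold.
- **Reporting (II.L.2).** Serious adverse events go to the coordinating center within 72 hours.
- **Withdrawal (II.D).** For the individual patient, the only listed reason for termination is the patient's own wish. "The withdrawn patients will be routinely followed on an outpatient basis in a clinic setting".

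**The concern.** A rule for leaving the study after an adverse event makes sense when treatment is continuing and stopping it can protect the patient. Here both planned doses are over when the wound is closed. For a DVT, PE or infection after that, ending participation changes only whether the trial goes on recording data.

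The decision is triggered by an event that is itself an outcome or is related to one, is taken without criteria, and includes someone who knows the allocation. Those are the conditions for informative loss that can differ between arms. What is at stake is the comparison of infection, PE and DVT rates that feeds the hold rule in II.L.1.e and supports the answer on safety promised in I.C, II.F.5 and V.B. To a smaller extent, so is the blood-loss comparison.

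**Working it through.** The plan gives no figure for serious adverse events, discontinuations or dropout, so there is nothing to reproduce. The check sets the sections side by side and then shows an illustration on assumed counts.

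**1. What ending participation can change.** Exposure is complete at closure (II.B). No test is done solely for research (II.E.3), and non-participants have the same tests and visits (III.E). For an event after closure, only trial data collection remains to be ended.

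**2. What happens to the patient's data.** II.D promises routine clinic follow-up but does not say that study data are still collected or analysed. II.L.1.b limits safety review to events in participating patients. Read literally, a PE that follows a DVT which ended participation falls outside it. No section defines an analysis population, a data-retention rule or a missing-data rule. II.D and II.L.3 also disagree on what can end participation.

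**3. Which outcomes are exposed.**

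| Data | Window | Exposed? |
|---|---|---|
| Triggering event | Reported within 72 hours (II.L.2) | Only if the patient is also dropped from the analysis |
| Later DVT, PE, infection | To 3 months (II.E.5) | Yes; this is the main exposure |
| Hemoglobin | 6 hours to postoperative day 3 | Only after an early in-hospital event with a quick decision, or if data are discarded |
| Drain output, transfusion | Recorded postoperatively | Same conditions as hemoglobin |

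Example: a DVT on day 2 may be reported as late as day 2 + 3 = day 5, after the last hemoglobin draw. At most the day 3 draw is at stake.

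**4. Illustration for the event comparison (assumed counts).** II.C gives 20 + 50 = 70 patients per arm. Assume 5 TXA and 2 control patients with venous thromboembolism.

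- All events kept: 5/70 − 2/70 = 7.14% − 2.86% = 4.3 points. There is no bias in this count.
- One TXA event patient dropped from the analysis: 4/69 − 2/70 = 5.80% − 2.86% = 2.9 points, a fall of about 31%.
- Two TXA event patients dropped: 3/68 − 2/70 = 4.41% − 2.86% = 1.6 points, a fall of about 64%.
- Two control event patients dropped instead: 5/70 − 0/68 = 7.1 points, so the difference grows.

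The last three lines require the patient to be dropped from the analysis, which the plan neither states nor rules out. They do not model later events missed because follow-up stopped.

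**5. Illustration for blood loss (assumed removal rates).** If the fraction q of one arm with the highest blood loss were dropped and blood loss were normal, that arm's mean would shift by −φ(z₁₋q)/(1 − q) SD. For q = 5%, 10% and 20% the fall is 0.11, 0.20 and 0.35 SD. With a correlation of 0.5 between removal and blood loss it is about half: 0.05, 0.10 and 0.18 SD. The first set is a worst case. If no data are dropped, the shift is zero.

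**The case against.** The strongest reply is that II.L.3 removes nobody. It says that continuation is to be decided, which includes continuing, and it says nothing about deleting data. Where the protocol wants a patient excluded it says so, as for non-standard dosing in II.B. An independent monitor is one of the three deciders. The triggering event is already due for reporting. Endpoint data come from the medical record (II.G), and withdrawn patients are still seen in clinic. Hemoglobin sampling is over by day 3, and missing draws after early discharge are already accepted.

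Most of this stands, and it limits the point. A reader might infer that the rule selectively removes the patients who carry the thrombosis and blood-loss information, or that a decision or two would erase most of a safety signal. The documents support neither. The first states a possibility as fact. The second needs the patient to be dropped from the analysis as well as from follow-up, and even then a single removal in the illustration costs about 31%. Nor is safety a formal aim: the aims, hypotheses and outcomes in I.A and II.A are blood loss, transfusion and drain output.

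What the reply does not supply is any text that keeps these patients in follow-up or in the analysis. Clinic visits and available records do not help if the trial no longer counts the patient as participating.

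**Conclusion.** The concern holds in a limited form. II.L.3 permits discretionary ending of participation after a serious adverse event, with unblinded input and no criteria, when exposure is already complete for any event after closure. II.D does not list this route, and no section secures continued data collection or analysis as randomized. The result is a possible outcome-dependent loss, mainly of later DVT, PE and infection events up to 3 months. The primary outcome is exposed only through early in-hospital events or discarded data.

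No size or direction of bias can be derived from the documents. The figures in the working rest on assumed counts and removal rates, the direction depends on which arm loses patients, and the effect is zero if nothing is dropped. The change is still worth making, because the rule offers no exposure benefit after closure and replacing it costs very little.

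**What to change.** In II.L.3, replace the participation decision with a statement that:

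- a serious adverse event does not end data collection;
- hemoglobin, drain, transfusion and complication data continue to be taken from routine care through the 3-month visit, unless the patient withdraws consent;
- the patient is analysed in the assigned group, and all data collected so far are kept.

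Reconcile this with the withdrawal criteria in II.D, which name only the patient's wish, and with the non-standard-dosing exclusion in II.B. Otherwise the protocol would hold conflicting rules on who leaves the study. In II.L.1.b, make clear that safety review covers every randomized patient. Clinical care after the event stays with the treating team and is not affected.

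The cost is a short amendment and slightly more record abstraction. No visits or tests are added, because all of them are already standard care (II.E.3, III.E).
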